9.3.2. Variables at Baseline

Patients included in the DUS will be described according to their characteristics at index date, using data from the baseline period, from diagnoses, procedures and prescription information from each data source:

- Age (as continuous variable and categories <18, 18-65, ≥65 years)
- Gender
- Diagnosis of IBS and type ¹
- Comorbidities:
 - o Cardiovascular disorders or risk factors—i.e., cerebrovascular disease, coronary artery disease, angina, myocardial infarction, heart failure, arrhythmias, use of antiarrhythmic drugs, hyperlipidaemia, or use of lipid-lowering drugs
 - o Hypertension or use of antihypertensive drugs
 - o Diabetes
 - o Hepatic impairment
 - o Chronic kidney disease or chronic renal failure
 - o Inflammatory bowel conditions (i.e., Crohn's disease, ulcerative colitis, microscopic colitis)
 - o Mechanical gastrointestinal obstruction
 - o Any psychiatric disorder, as well as:
 - Depression diagnosis
 - Anxiety diagnosis
 - o Food intolerance (e.g., lactose)
 - o Celiac disease
 - o Cancer (e.g., colon)
 - o Bile salt malabsorption
 - o Immunodeficiency

¹ When possible, proportion of IBS-C.

- Obesity and eating disorders (anorexia nervosa, bulimia)
- Medications: the three most commonly prescribed medication groups in addition to the following, if not included (Only about half of IBS-C patients are expected to be on prescribed medication, but the majority of patients are expected to be self-treated [Wilson et al., 2004].):
 - Laxatives (i.e., bulk-forming laxatives, stimulant laxatives, faecal softeners, and osmotic laxatives) (Concomitant use of laxatives was described among one-third of the antispasmodic mebeverine users and it was associated with increased odds of hospitalisation [Goettsch WG, 2004].)
 - Antispasmodics (i.e., anti-muscarinic agents and direct-action smooth muscle relaxants)
 - Prokinetic drugs
 - Antidepressants (i.e., tricyclic antidepressants, selective serotonin reuptake inhibitors, serotonin-norepinephrine reuptake inhibitors, and monoamine oxidase inhibitors)
 - Antibiotics
 - Calcium and aluminium-containing antacids
 - Magnesium-containing antacids
 - H2 blockers
 - Proton pump inhibitors
 - Analgesic drug classes:
 - Non-steroidal anti-inflammatory drugs
 - Opioids
 - Other analgesics
- Other variables:
 - History of digestive surgery (especially history of cholecystectomy)
 - Gastroenterology clinic visit (Spain and Sweden) or referral (UK)

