projected number of patients	518	1211	2,674
projected number of patients-years	211	557	1,219
SIDIAP: 12.8% of Spain			
projected number of patients	207	1,108	2,407
projected number of patients-years	76	456	1,122
Sweden National Patient Register: 95% of Sweden			
projected number of patients	1,147	2,766	4,584
projected number of patients-years	506	1,250	2,231
Combined:			
projected number of patients	1,872	5,085	9,665
projected number of patient-years	794	2,263	4,572

*86% in Sweden and Spain, 81% in the UK, of the total number of linaclotide users
Abbreviations: CPRD=clinical practice research datalink; UK=United Kingdom

By the end of 2016 it was estimated that over 9,650 patients would have been exposed to linaclotide

in the three target databases together, for a combined exposure of more than 4,500 patient years. The UK would be contributing approximately 28% of patients, Spain 25%, and Sweden 47%.

For the treatment patterns, a total of approximately 8,800 patients would allow the detection of a hazard ratio of 1.2 or greater for patient characteristics, assuming linaclotide discontinuation or linaclotide switching occur in about 10% the observed sample (users with a specific characteristic) with a probability of 40%, with 90% power and a two-sided type I error rate (alpha) of 5%.

In the progress report for 2016, users of linaclotide included in each of the study databases were reported to be below the targeted numbers. Following the recommendation of the PRAC rapporteur, the end of the data collection was then extended by one year until December 2017 to allow for the number of users to reach the desired sample size.

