To better assess differences in time to event by the alleged reason for linacotide prescription (IBS-C or other conditions), Cox regression analysis will be employed. Multivariate Cox regression models will be fitted to identify the effects of the indication and various other baseline variables on the time from initiation of linacotide to first treatment discontinuation or switching. For each of the two outcome variables (time to discontinuation and time to switching), a set of plausible candidate models will be proposed and fitted to the data. Models will be ranked according to Akaike's Information Criterion and the best model will be selected; or, if several models prove to perform well, these will be averaged to produce a final model. Some iteration between choosing candidate models and data analysis will likely be necessary, owing to the need to check that the proportional hazards assumption holds for each candidate model.

Statistical analyses will be conducted using SAS® statistical software.

9.8. **Quality Control**

Standard operating procedures at each research centre will be used to guide the conduct of the study. These procedures include internal quality audits, rules for secure and confidential data storage, methods to maintain and archive project documents, quality-control procedures for programming, standards for writing analysis plans, and requirements for senior scientific review.

All work will be subject to quality control and documentation procedures to make certain the final report is accurate and thorough and the analyses can be reproduced. If the data do not permit an analysis as planned (e.g., through insufficient sample size in a subgroup analysis) or if clarifying analyses are required (e.g., an unexpected result that could be explained by a subgroup analysis), [REDACTED] staff will inform Allergan and include the additional information and results in the report. All key study documents, such as the analysis plan, abstraction forms, and study reports, will undergo quality-control review, senior scientific review, and editorial review.

A quality-assurance audit of this study may be conducted.

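### The 90% power for HR 1.2 in section 9.5 makes no allowance for covariate adjustment, although section 9.7.2 estimates the effects in multivariable Cox models

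*Protocol*

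**What the plan says.** Protocol section 9.5 (Study Size) sizes the treatment-pattern analysis by stating that "a total of approximately 8,800 patients would allow the detection of a hazard ratio of 1.2 or greater for patient characteristics". The assumptions are that discontinuation or switching "occur in about 10% the observed sample (users with a specific characteristic) with a probability of 40" per cent, "with 90% power and a two-sided type I error rate (alpha) of 5" per cent. No correlation with other covariates, variance inflation or adjustment is mentioned.

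Section 9.7.2 (Linaclotide Prescription Patterns) then sets the analysis: "Multivariate Cox regression models will be fitted to identify the effects of the indication and various other baseline variables" on time to first discontinuation or switching. Candidate models are to be proposed for each outcome, ranked by Akaike's criterion, and the best one selected or several averaged.

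Two further statements bear on N. Section 9.7 has the analyses run in each country separately, and section 4.9 adds aggregated analyses only for the primary objectives. Treatment patterns are secondary (sections 8.1 and 9.3.3). Section 9.5 also reports that in 2016 "users of linaclotide included in each of the study databases were reported to be below the targeted numbers".

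**The concern.** The power statement is for one binary characteristic considered alone. The planned estimate for that characteristic comes from a model that contains other baseline variables. When the characteristic is correlated with those variables, the variance of its log hazard ratio is inflated by 1/(1 − R²), where R² is its squared multiple correlation with the other covariates. The sizing is exact at R² = 0 and has almost no slack, so any material correlation takes the adjusted estimate below the stated 90%.

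At stake is how a reader interprets an adjusted hazard ratio near 1 for a characteristic carried by about one user in ten. Section 9.5 invites the reading that the study had 90% power for HR 1.2, and the adjusted model would have less.

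**Working it through.** **Inputs from section 9.5.** HR 1.2; two-sided alpha 5% (z = 1.960); power 90% (z = 1.2816); prevalence of the characteristic 10%, so p(1 − p) = 0.1 × 0.9 = 0.09; event probability 0.40; N about 8,800. Projected numbers at the end of 2016 (Table 3): UK 2,674, Spain 2,407, Sweden 4,584, combined 9,665.

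**Input not in the documents.** R² is an assumption here, shown from 0 to 0.5. HR 1.2 is taken as the adjusted effect.

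**1. Reproduce the plan's figure (Schoenfeld formula, no covariates).**

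Events = (1.960 + 1.2816)² / (0.09 × (ln 1.2)²) = 10.507 / (0.09 × 0.03324) = 3,512.

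Patients = 3,512 / 0.40 = 8,780, in agreement with 8,800. One-sided alpha (7,158), 80% power (6,560), a 1:1 split (3,163) and swapping the 10% and 40% (13,180) do not match.

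**2. Slack left for adjustment.** 1 − 8,780/8,800 = 0.002. If the 40% is read as the event risk in patients without the characteristic, the formula gives about 8,654, and the slack is 1 − 8,654/8,800 = 0.017. Either way it is negligible.

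**3. Power and detectable HR at N = 8,800.**

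Power = Φ(√(0.4 × N × 0.09 × (1 − R²)) × ln 1.2 − 1.96).

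Detectable HR (90% power) = exp(3.2415 / √(0.4 × N × 0.09 × (1 − R²))).

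N for 90% power at HR 1.2 = 8,780 / (1 − R²).

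| Assumed R² | Power at 8,800 | Detectable HR | N needed (about) |
|---|---|---|---|
| 0 | 90.1% | 1.20 | 8,780 |
| 0.05 | 88.6% | 1.21 | 9,240 |
| 0.1 | 86.8% | 1.21 | 9,760 |
| 0.2 | 82.7% | 1.23 | 10,980 |
| 0.3 | 77.5% | 1.24 | 12,540 |
| 0.5 | 63.1% | 1.29 | 17,560 |

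Example at R² = 0.3: 0.4 × 8,800 × 0.09 × 0.7 = 221.8, whose square root is 14.89. Then 14.89 × 0.1823 − 1.96 = 0.755, and Φ(0.755) = 77.5%.

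The loss against 90% stays within 2 points up to an R² of about 0.067. The projected 9,665 would hold 90% up to R² = 1 − 8,780/9,665 = 0.09, but accrual was reported below target.

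**4. The same formula at the N of the by-country models.** These use the Table 3 projections, 10% prevalence and a 40% event probability.

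| Country | N | HR at R² = 0 | HR at R² = 0.1 | HR at R² = 0.3 |
|---|---|---|---|---|
| UK | 2,674 | 1.39 | 1.42 | 1.48 |
| Spain | 2,407 | 1.42 | 1.44 | 1.52 |
| Sweden | 4,584 | 1.29 | 1.30 | 1.35 |

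Example for the UK at R² = 0.1: 0.4 × 2,674 × 0.09 × 0.9 = 86.6, square root 9.31, and exp(3.2415/9.31) = 1.42.

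**5. How far this depends on the 10% prevalence.** At 8,800 patients, 90% power needs p(1 − p)(1 − R²) of at least 0.09 × 8,780/8,800 = 0.0898. At R² = 0.3, p(1 − p) must reach 0.0898/0.7 = 0.128. A prevalence of 16% already gives 0.134. At an assumed 30% prevalence and R² = 0.3, power is about 98.6%.

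**The case against.** The strongest reply is that nothing in section 9.5 is miscalculated. The stated inputs give the stated N, the protocol does not claim that the power is for an adjusted effect, and sizing on a single covariate is a common simplification. The study is described as descriptive with no a priori hypothesis (section 7), and R² appears nowhere, so the size of the loss is assumed. All of that stands. It limits the point to an overstated power statement for a secondary outcome. It does not remove the mismatch, because 9.5 speaks of effects of patient characteristics and 9.7.2 estimates those effects by multivariable models. An unadjusted Cox comparison by indication is not excluded by 9.7.2, but that does not cover the other characteristics.

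Three stronger readings are tempting, and the documents do not support them.

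- A reader might infer that the baseline list in section 9.3.2 guarantees overlap, since it has "Any psychiatric disorder, as well as" depression and anxiety, and "Hypertension or use of antihypertensive drugs" beside cardiovascular risk factors. That section lists variables for describing patients. It is not a list of Cox covariates, and the candidate models are still to be proposed. Some correlation is plausible, but neither its presence in a given model nor its size is fixed, and nothing written puts a psychiatric flag and its subset in one model. The female predominance in section 7 concerns IBS in general and does not establish a correlation among linaclotide users.
- A reader might infer that the comparison by indication (IBS-C versus other) falls short of 90%. The 10% prevalence is stated for a generic characteristic, and the indication split is not given. At middling prevalences, pooled power would exceed 90% even at R² = 0.3 (step 5 of the working).
- A reader might take 1.21 to 1.24 as what the study can detect. Those values use the pooled 8,800, whereas the treatment-pattern models are run by country.

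**Conclusion.** The point holds, as a matter of labelling and restating a figure. For a characteristic near 10% prevalence with a 40% event probability, the 90% power for HR 1.2 at about 8,800 patients belongs to an unadjusted, pooled comparison. The adjusted analysis in section 9.7.2 has less: about 87% to 78% at that N for an assumed R² of 0.1 to 0.3, and under 2 points less than stated if R² is below about 0.07. The direction is certain for any R² above the negligible slack, but the size rests on an R² that the documents do not give. The consequence is an overstated power statement in a descriptive study, not a failed confirmatory test. That the models are run by country is a separate and larger limitation. It enters here only because a restated detectable HR must use the right N.

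**What to change.** In section 9.5:

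1. State that the 8,800 patients, HR 1.2 and 90% power apply to an unadjusted hazard ratio and to the pooled total across databases.
2. Add the detectable adjusted HR as exp(3.2415 / √(0.4 × N × 0.09 × (1 − R²))) over a stated R² range, with N taken from the analysis actually run. At the projected country sizes and R² of 0.1 to 0.3 this gives about 1.42–1.48 (UK), 1.44–1.52 (Spain) and 1.30–1.35 (Sweden). Update N to the counts reached by the extended data cut.
3. Say that the 0.09 reflects 10% prevalence, and replace it by p(1 − p) for characteristics with another prevalence, including indication.

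The cost is a few lines of protocol text and a less favourable stated detectable effect. No extra patients, data or analyses are needed.

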4.9. Data Analyses

All analyses will be first performed separately in each of the study countries. In addition, for the primary study objectives, aggregated analyses with data from all three countries will be performed.

Baseline analyses will be conducted to characterise linaclotide users, and socio-demographic and clinical variables will be described for all users and for those subgroups of patients who were not sufficiently documented in the clinical development programme. The number and percentage of patients using linaclotide off-label will be also described.

Further, linaclotide treatment patterns will be described from index date to end of study period for linaclotide utilisation. Kaplan-Meier estimates will be used to describe time to discontinuation in the prescription or dispensation of linaclotide; and to describe switching from linaclotide to another drug used in IBS-C (laxatives, antispasmodics, prokinetics, or antidepressants). To better assess differences in time to event by the alleged reason for linaclotide prescription (IBS-C or other condition), Cox regression analysis will be employed if the proportional hazards assumption holds; if not, more complex models will be proposed, including predictor variable interactions with time.

Statistical analyses will be conducted using SAS® statistical software.

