 - Bacterial/viral/parasite lab information, when available (positive versus negative or no information)

For prevalence of chronic comorbidities, prior diagnoses, or history of digestive surgery at index date, the patient's entire medical history will be explored.

9.3.3. *Linaclotide Treatment Outcomes*

Secondary outcomes of this study will be linaclotide treatment patterns. The linaclotide exposure information is characterised by the linaclotide days of supply. Days of supply will be ascertained from the prescription/dispensation information recorded in the databases and the recommended dose (one capsule of linaclotide 290 µg taken once per day) and calculated by dividing the quantity prescribed/dispensed by the daily dose. Days of supply of one prescription/dispensation are expected to be around 28 days since the 28-capsule pack will be the most widely used package size. If package size is unknown, then the median duration for patients with this information will be used (and if no median can be estimated then 28 days will be used).

Linaclotide prescription patterns of interest are:

- Discontinuation of linaclotide: defined as no prescription of linaclotide in the period of 1.5 times the number of days of supply of the last linaclotide prescription following its expiry date (Sikka et al., 2005; Peterson et al., 2007): for example, for a 28-day prescription, no new prescription in the 43 days after the expiry date of the prescription supply. The date of discontinuation is the day after the date of expiry of the last linaclotide prescription. Time to discontinuation (permanently during the study period or temporarily) is the interval between the date of the first linaclotide prescription and the date of discontinuation. Discontinuation

will be reported separately for those who permanently discontinue during the study period and for those who discontinue temporarily and subsequently restart on linaclotide (see below).

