9.7. Data Analysis

Analyses will be performed in each of the study countries separately.

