SIDIAP is a primary care database launched in 2010, following the steps of CPRD or THIN in the UK, that collects longitudinal data from EMR from 274 primary care centres in Catalonia since 2006. Catalonia is a region with a total of 5.8 million patients who represent approximately 12% of the Spanish population (4% of the Spanish population in SIDIAP-Q with higher quality indicators). Data is updated once a year and there are several scientific publications using this data source and reporting validation study results. The date of the latest available data is December 2013, and 2014 data will be made available by May–June 2015.

Data from primary and specialised care, hospital and pharmacy data are available, as well as patient characteristics such as gender and date of birth, GP-diagnosed conditions, GP prescriptions, prescription dosing and size, date of prescription and dispensation, laboratory test results, other procedures, specialist referrals and diagnosis, hospital referrals, hospital procedures, and discharge diagnosis death rate, and pregnancy information. GP diagnoses are coded following the ICD-10 codes, and hospital admissions following the ICD-9.

SIDIAP does not transfer data to private entities, but it can carry out quality investigation projects (Bolívar et al., 2012) and submit on their completion the corresponding reports on results, which will be agreed upon with the funding body in the design stage of the study. It also allows the possibility to contact physicians (currently a group that includes 10% of the total) for extracting additional information on the patient through a questionnaire.

SIDIAP is considered to be an appropriate source of data for the execution of this as the vast majority of its patients have two and three or more years of follow-up and the database itself can link with the Drug Dispensation databases (and additionally with the Mortality Registry for Death Cause); both characteristics are relevant for the proposed linaclotide study. The objectives were reviewed by their research team who are confident about the utilisation study. They identified some challenges for the safety study, and recommended performing a preliminary descriptive and exploratory study to confirm feasibility of conducting the study and to improve the validity of the actual study results.

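### Section 9.5's 90% power for a hazard ratio of 1.2 needs all three databases combined, but the protocol plans the treatment-pattern models country by country

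*Protocol*

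**What the plan says.** **Power statement.** Protocol section 9.5 says that, for treatment patterns, "a total of approximately 8,800 patients would allow the detection of a hazard ratio of 1.2 or greater" for patient characteristics. Power is 90% and alpha 5% two-sided. The remaining inputs are awkwardly worded: events are said to "occur in about 10% the observed sample (users with a specific characteristic) with a probability of 40" per cent. I read this as 10% of users having the characteristic and 40% having the event.

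**Projected sizes.** Table 3 projects 2,674 patients in the UK, 2,407 in Spain and 4,584 in Sweden by the end of 2016, 9,665 in all. Section 9.5 adds that users in each database then ran below target, so data collection was extended to December 2017.

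**Unit of analysis.** Section 9.7 opens with "Analyses will be performed in each of the study countries separately". The abstract (section 4.9) says separate analyses come first and adds that "for the primary study objectives, aggregated analyses with data from all three countries will be performed".

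**Status of the endpoints.** Section 9.3.3 says "Secondary outcomes of this study will be linaclotide treatment patterns", and names time to discontinuation and time to switching as secondary endpoints. Section 8.1 makes prescription patterns the secondary research question. Section 9.7.2 describes the Cox models without a country term, a pooled fit or a combination of country estimates.

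**The concern.** A power figure is informative only for the analysis it describes. The 8,800 patients exceed any single country's projection, so the sentence must refer to all three databases together. Yet the protocol provides aggregation for the primary objectives and does not extend it to the secondary endpoints to which the sentence is attached.

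What is at stake is interpretation. Section 8.2 makes the effect of indication on time to discontinuation or switching an objective. If one country's model shows no clear association, a reader who looks up the planned power will find 90% for a hazard ratio of 1.2, when the figure for that country's model may be far lower. The extension to December 2017 was justified by reaching the desired sample size, so it matters whether that size refers to a planned analysis.

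**Working it through.** **1. Reproduce the plan's figure.** Inputs from section 9.5: HR 1.2, prevalence p = 0.10, event probability 0.40, two-sided alpha 5%, power 90%. Schoenfeld's formula gives

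events = (1.960 + 1.282)² / [p(1 − p) × (ln 1.2)²] = 10.507 / (0.09 × 0.03324) ≈ 3,512

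patients = 3,512 / 0.40 ≈ 8,780

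This matches the stated 8,800 and supports the reading of the inputs given above.

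**2. Compare with the sizes available.** The largest country is Sweden at 4,584. Only the combined 9,665 exceeds 8,800.

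**3. Power by country for HR 1.2, at 10% prevalence.** Power = Φ(ln 1.2 × √(p(1 − p) × 0.40 × n) − 1.960). The HR detectable with 90% power is exp(3.242 / √(p(1 − p) × 0.40 × n)).

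| | n (Table 3) | Events (0.40n) | Power | HR detectable with 90% power |
|---|---|---|---|---|
| UK | 2,674 | 1,070 | 43% | 1.39 |
| Spain | 2,407 | 963 | 40% | 1.42 |
| Sweden | 4,584 | 1,834 | 65% | 1.29 |
| Combined | 9,665 | 3,866 | 92.5% | 1.19 |

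**4. Dependence on prevalence.** Same formula and same Table 3 sizes; power for HR 1.2:

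| Prevalence | UK | Spain | Sweden |
|---|---|---|---|
| 10% | 43% | 40% | 65% |
| 20% | 66% | 62% | 88% |
| 30% | 78% | 74% | 95% |
| 50% | 85% | 81% | 97% |

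Sweden passes 90% at a prevalence of about 23%. Because p(1 − p) is largest at 50%, the UK and Spain cannot reach 90% at these sizes for any binary characteristic.

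**5. Does the extra year close the gap?** As an upper bound on the protocol's forecasts, count every 2017 user in Table 2 as new, with Table 3 coverage and 90% eligibility:

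- UK: 2,674 + 45,279 × 0.08 × 0.9 = 5,934; power 76%
- Spain: 2,407 + 23,073 × 0.128 × 0.9 = 5,065; power 69%
- Sweden: 4,584 + 4,052 × 0.95 × 0.9 = 8,048; power 87%

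These powers are at 10% prevalence. No country reaches 8,800 patients or 90%. The bound is generous, because many 2017 users would be continuing patients and recruitment to the end of 2016 was below forecast.

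**6. Would combining estimates recover the stated power?** With a common hazard ratio and equal prevalence, each country's log HR has information p(1 − p) × events, and inverse-variance weighting adds these: 0.09 × (1,070 + 963 + 1,834) ≈ 348. Power = Φ(0.1823 × √348 − 1.960) ≈ 92.5%, the same as the combined row above. No patient-level pooling is needed.

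**The case against.** The strongest reply is that little hangs on the sentence. Section 7 calls the study descriptive with no a priori hypothesis, the endpoints are secondary, no decision rule uses the power figure, and no estimate is biased. That stands, and it limits the severity. It does not make the sentence consistent with the analysis: section 9.5 makes a formal power claim for models that section 9.7.2 fits.

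A second reply is that the statistical analysis plan may combine countries. How to combine is indeed a matter for that document. But the protocol itself limits aggregation to the primary objectives, so the inconsistency lies within the protocol.

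Four stronger readings are tempting and are not supported:

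- *No planned Cox model has 90% power.* This holds at 10% prevalence only. The protocol gives no prevalence for indication (IBS-C or other), the main covariate. Sweden reaches 90% at about 23%, and at the generous 2017 sizes all three countries exceed 90% at 20% prevalence (UK 94%, Spain 91%, Sweden 98.5%).
- *The protocol promises 90% power in each country.* It does not. It speaks of a total, directly after giving the combined projection.
- *Patient-level pooling is impossible for Spain.* Annex 3 says only that "SIDIAP does not transfer data to private entities". The analysing organisation is redacted, so whether this restriction applies to it cannot be established, and section 4.9 already foresees some form of aggregation.
- *The ENCePP checklist confirms that treatment patterns will never be combined.* Its comment about separate analyses sits under Data Sources, not under Analysis Plan, and does not say that they are the only analyses.

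**Conclusion.** The point holds as an internal inconsistency that should be fixed. The 8,800 is correctly calculated, but it describes a three-database analysis of endpoints that the protocol analyses by country. On section 9.5's own inputs, the country models have about 43%, 40% and 65% power for a hazard ratio of 1.2 at Table 3 sizes, and at most 76%, 69% and 87% on the generous 2017 count.

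These figures assume 10% prevalence, proportional hazards, no loss of information from adjusting for other covariates, and the full 40% event probability for each outcome. If the 40% covers discontinuation and switching together, each separate model has fewer events and lower power. More common characteristics have higher power, as shown in the working. The shortfall in the UK and Spain at Table 3 sizes does not depend on the 10% assumption; the one in Sweden does.

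**What to change.** Choose one of two changes.

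1. **Combine.** State in sections 4.9 and 9.7.2 that the country-specific log hazard ratios for treatment patterns will be combined, for example by inverse-variance weighting with heterogeneity reported. The covariate must be defined and modelled in the same way in each country. Say in 9.5 that the 8,800-patient power applies only to that combined estimate, at 10% prevalence. This needs three estimates and their standard errors, with no transfer of patient data.
2. **Restate.** Replace the sentence in 9.5 with country-specific detectable hazard ratios and name the prevalence assumed. At 10% prevalence, 40% events and Table 3 sizes, the values for 90% power are 1.39 (UK), 1.42 (Spain) and 1.29 (Sweden). Update them to the actual counts, since the projections were not met.

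Either way, the cost is a sentence or two of text. The downside is that the precision stated for each country looks less favourable than the present sentence suggests. Data collection and the primary analyses do not change.
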